Aim 2:, we will conduct the first randomized controlled trial (RCT) to telemonitor minority community-dwelling patients with CHF (NYHA class1-3) for 3 months after hospital discharge for CHF. We will compare hospital and emergency room utilization, as well as QoL, between TSM and standard of care groups.

According to the NYHA classification system, patients experience increased limitations in physical activity, such as fatigue, palpitation and angina pain, from mild in class 1 to extreme in class 4. Patients in class 4 experience these symptoms even at rest, and are usually bedbound. We specifically excluded seniors with heart failure NYHA class 4 because they are primarily bed-bound and highly unlikely to be able to participate in the tasks required of the intervention.

Specifically, after hospitalization for a CHF exacerbation at NUMC, patients will be approached by the heart failure clinic nurse to assess interest in participation. The study will be described in detail, and patients will be assured of confidentiality. Once patients give permission, the clinic nurse will personally introduce the patient to the research nurse, and reiterate their willingness to participate, the formal consent process will occur. Patients will be randomized once they have given consent to participate in the study.

EXPERIMENTAL DESIGN

Aim 1: we will conduct a process evaluation to assess telehealth acceptance and usability among low-income, largely minority seniors living with CHF NYHA class 1-3.

We will assess usability of an existing Heart Failure telehealth intervention and will adapt the intervention to facilitate acceptability and feasibility in a population of low-income ethnic minority patients. Usability will be assessed throughout the study period through the examination of usability indicators presented temporally below.

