
1b. Patient Usability (patient perspective): We will also conduct a focus group with the initial 10 patients enrolled in the intervention arm of the study to obtain user feedback regarding any barriers to implementation or usability suggestions to further adapt the intervention if necessary before additional participants are enrolled. The qualitative methods detailed above will be employed. The patient focus group will take approximately two hours and will be conducted in a confidential conference room at NUMC. Patient participants will be compensated \$50 for their participation. The discussion guide for the patient focus group will be developed by the Drs. [name] and [name] with input from the CAB (see Appendix 2). Discussion topics include (but are not limited to) the following: 1) patients' perceptions of the ease of the study implementation (using the equipment, uploading) 2) patients' perceptions of usefulness of the intervention; 3)

patients' input on barriers/challenges to intervention implementation; and 4) suggestions for improvements and/or adjustments that should be made. Data will be coded and analyzed using NVivo (see above) to identify the barriers and challenges that need to be addressed as study implementation continues in order to ensure a high level of usability.

Patient Utilization: This phase of intervention development will also involve an ongoing process evaluation of usability using quantitative methodology. Again, this is so that adjustments can be made, as necessary, as the TSM intervention is implemented.

We will operationalize usability using the following measures:

- 1) Rate of acceptability
- 2) Rate of installation acceptance
- 3) Upload compliance
- 4) Total number of visits
- 5) Patient satisfaction

Aim 2: we propose to conduct the first randomized controlled trial to telemonitor minority community-dwelling patients with CHF (NYHA class1-3) for 3 months after hospital discharge or CHF. We will compare hospital and emergency room utilization, as well as QoL, between TSM and standard of care groups.

This is a prospective randomized controlled trial of 104 community-dwelling patients from disparity communities living with CHF 18 years and older.

In this study, patients will be randomized either to TSM or to standard of care once they have given consent to participate to *directly compare TSM to standard of care* in a health disparity population.

Table 1. Proposed Intervention: TSM and Standard of Care (SOC)		

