When discharge from NUMC is imminent, [name], NP, the Director of the NUMC Heart Failure Clinic, will review the study with the patients and consent will be obtained if the subject is willing to be part of the study. The study will be described in detail, and patients will be assured of confidentiality. Once patients give permission (in writing) to discuss the study, the clinic nurse will personally introduce the patient to the bi-lingual research nurse (TBA), and reiterate their willingness to participate, the formal consent process will occur. The research nurse will discuss the study with the patient, including a discussion of the overall goals of the study, the study design, the study time frame (3 months), and the randomization procedures. The nurse will also gather basic information regarding inclusion and exclusion criteria (ex., NYHA class). If the patient meets the inclusion criteria, the nurse will read the consent form aloud, in the patient's primary language, which contains information regarding confidentiality of protected health information, the de-identification of data, risks and benefits of study participation and a description of compensation for participation. The nurse will explain that the information collected regarding daily health could be shared with the patient's physician when necessary, but is completely de-identified for research purposes and will not be shared with anyone else at any time. The consent form will also underscore that the patient can withdraw from the study at any time with no consequences. The nurse will also make sure that the patient understands that he/she will be randomized to either the telehealth self management (TSM) intervention or a control group which is standard of care. However, the nurse will explain to the patient that enrollment for the telehealth arm of the study has ended and he/she will be enrolled in the standard of care arm. If the patient agrees to participate, she/he will be asked to sign an informed consent form. The informed consent will comply with all HIPAA and IRB requirements. We will conduct a block randomization technique to ensure equivalency of gender and Heart Class 3 patients across the two groups. Patients will be randomized by the Feinstein

Biostatistics Unit, as utilized in our previous studies. CAB members and patients who participate in the focus groups will be compensated \$50. Patients in both arms of the RCT will receive \$100 for participation.

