Upload compliance: We are arbitrarily defining three levels of compliance: High, moderate and minimal. "Minimal" compliance is defined as at least one upload per week for 6 out of the 12 weeks. "Moderate" compliance is defined as at least one upload per week for 9 out of the 12 weeks, and "High" compliance is defined as at least three uploads per week for 9 out of the 12 weeks. *A secondary compliance measure will be the number of uploads over* the 90 day period. = u/d. (maximum number of possible uploads = 90). All of these measures will be appropriately prorated for patients who die, or are hospitalized during the study, and are therefore not subject to uploading requirement during those times. With a sample size of 52 patients, the rates of compliance can be estimated to, at worst, +- 13.9%, with a 95% CI.

Total number of visits: We will compute the proportion of 12 scheduled visits that are kept. Therefore, if a patient is being followed for *w* weeks, there should be *w* scheduled visits. If the number scheduled visits that are kept is denoted by *v*, then the proportion of scheduled visits kept = v/w. Visit participation rates will be averaged across patients, and the mean rate will be computed, along with 95% confidence intervals. There is a maximum of 12 possible telehealth visits over the 3 month study period.

Patient satisfaction: We will measure patient perceptions of usability using a slightly modified version of the Telemedicine Satisfaction and Usefulness Questionnaire (Appendix 3). This 22-item questionnaire, which utilizes a 5 point Likert scale, will elicit a total sum score of satisfaction/usability that will then be dichotomized into satisfied vs. not satisfied based on previous literature.

Sample size considerations: We will randomize 116 patients as they are discharged from the hospital (58 per arm) in order to yield a maximum of 52 patients in the TSM arm of the study over a two year period.

These scores will be assessed using mean scores, percentages and histograms.²⁵ For satisfaction rates of 50%, 75% and 90%, with a sample size of 52, the corresponding 95% confidence intervals will have precision of +/- 13.9%, 12.7%, and 8.3%, .

Aim 2: we will measure inpatient utilization, emergency room utilization and QoL of patients receiving telehealth technology vs. standard of care patients.

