2a. Measures of Inpatient Utilization. Inpatient utilization will be measured in three ways, including: 2a.1) whether an individual subject had at least one inpatient hospitalization over the 3 month period; 2a.2) the number of hospitalizations experienced by an individual subject over the 3 month period; and 2a.3) cumulative length of stay (LOS) (inpatient days) experienced by an individual subject over the 3 month period (i.e., for multiple hospitalizations, the sum of all LOS's will be computed as the cumulative LOS). Cumulative LOS will be analyzed in two ways: intention to treat (ITT) analysis, and for only those hospitalized. The ITT analysis will include all patients, regardless of hospitalization history, to address the bigger public health issue: does TSM have an impact on LOS overall? A secondary analysis will look at LOS only for those who experienced a hospitalization. Finally, after ITT analysis, secondary analyses will include covariate adjustments for possible confounders.

Statistical Methods: Inpatient Utilization. For outcome 2a.1, the proportions of patients in each group who were hospitalized will be compared using the standard Chi-square or Fisher's exact test. Associated 95% confidence intervals for these proportions and their differences will be computed using exact methods. For outcome 2a.2, the number of hospitalizations will be compared using Poisson regression (SAS PROC GENMOD). It is likely that, due to excess zeros (i.e., zero inflation), methods for overdispersed Poisson will be required. Another approach for both outcomes 2a.2 and 2a.3 will be to use Lachenbruch's two stage procedure for zero-inflated data.30 For these primary ITT analyses, no adjustments will be made for any covariates.

Sample size considerations: We expect to enroll 52 patients in the TSM group which will yield the necessary statistical power.

2b. Measures of ER Utilization, defined as: 2b.1) whether or not an individual subject had at least one ER visit over the 3 month period; and 2b.2) the number of ER visits experienced by an individual subject over the 3 month period. Covariate adjustments will be made for potential confounders.

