## A Randomized, Controlled Trial Comparing Telehealth Self-Management to Heart Failure Clinic Outpatient Management in Black and Hispanic Disparity Patients Living with Heart Failure

[name], [name], MA, [name], [name], [name], [name], NP, [name], MS, [name], [name], [name], LMSW, [name], MSN, [name], and [name], MPH

The health system's Biostatistics Unit created a randomization schedule for patient assignment, to randomize patients to either TSM or COM using permuted block randomization, with stratification by heart class, to ensure equal representation of heart class across the two groups. The primary analysis of this randomized clinical trial was based on intention to treat (ITT) principle, which included all subjects randomized. Descriptive statistics are presented as means, standard deviations, medians, ranges and frequency/percentages.

Inpatient utilization was defined in three ways, including: 1) whether an individual patient had at least one inpatient hospitalization over the 90 day period; 2) the number of hospitalizations experienced by an individual patient over the 90 day period; and 3) the cumulative length of stay (LOS) (inpatient days) experienced by an individual patient

over the 90 day period (i.e., for multiple hospitalizations, the sum of all LOS's was computed as the cumulative LOS).

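### The recruitment text randomizes patients and also assigns them directly to standard of care after the telehealth arm closes, and the SAP does not say whether such patients are in the primary comparison

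*Protocol*

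**What the plan says.** Three statements stand in one paragraph of the protocol's Recruitment Procedures:

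- The nurse makes sure the patient understands that "he/she will be randomized to either the telehealth self management (TSM) intervention or a control group which is standard of care".
- The next sentence has the nurse explain that "enrollment for the telehealth arm of the study has ended and he/she will be enrolled in the standard of care arm". The consent signature comes after this.
- The paragraph then describes block randomization balancing gender and heart class 3, carried out by the biostatistics unit.

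Elsewhere the plan describes randomization only. The Specific Aims (Aim 2) state: "Patients will be randomized once they have given consent to participate in the study". The Experimental Design (Aim 2) says that "patients will be randomized either to TSM or to standard of care once they have given consent to participate". The Aim 1 sample size paragraph plans 116 randomized, 58 per arm, with no control-only phase.

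On analysis, the protocol's inpatient utilization methods say: "For these primary ITT analyses, no adjustments will be made for any covariates". The SAP's opening paragraph describes a permuted-block schedule to the two arms, stratified by heart class, and continues: "The primary analysis of this randomized clinical trial was based on intention to treat (ITT) principle, which included all subjects randomized". It does not mention closure of the telehealth arm.

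**The concern.** A patient cannot be both allocated at random between two arms and told before consent that only one is open. Anyone enrolled under the second statement is a non-randomized, non-concurrent control. Such patients may differ from the TSM group because they accepted a study already knowing they would get usual care, and because they were discharged in a later period.

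If they are analyzed as controls, those differences enter the between-arm comparison and are read as an effect of TSM. The primary comparison is unadjusted, so nothing in it would offset them. The direction of the bias cannot be predicted. Whether all analyzed controls were randomized alongside the TSM patients is a basic question for this trial, and the documents do not let a reader answer it.

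**Working it through.** **Status of a patient enrolled after closure**

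| Source | What it implies |
|---|---|
| Recruitment Procedures, first and third statements | Randomized |
| Recruitment Procedures, second statement | Assigned directly to standard of care |
| Specific Aims and Experimental Design, Aim 2 | Every consenting patient is randomized |
| Aim 1 sample size paragraph | 58 per arm, all randomized |
| SAP, opening paragraph | Analyzed if randomized; closure not mentioned |

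The SAP's rule turns on the word randomized, and the protocol applies that word to these same patients. The rule therefore does not classify them reliably.

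**Inputs for size**

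- From the SAP's sample size paragraph: 75% versus 50% hospitalized at least once, two-sided alpha 0.05, chi-square test, 52 per group.
- Assumed: k, the number of directly assigned patients among 52 analyzed controls; D, the difference between their 90-day hospitalization risk and that of randomized controls; and a common risk of 60% with no true effect when computing false-positive rates.

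**The plan's own figure.** No power is stated for the hospitalization outcome. With pooled variance under the null, power at 52 per group is Φ[(0.25 − 1.96·SE₀)/SE₁], where

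- SE₀ = √(0.625 × 0.375 × 2/52) = 0.0949
- SE₁ = √(0.25/52 + 0.1875/52) = 0.0917

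This gives Φ(0.697) = 75.7%.

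**If k such patients are kept.** The control rate shifts by (k/52) × D. False-positive rates come from exact enumeration over both arms, with TSM events Bin(52, 0.60) and control events Bin(52 − k, 0.60) + Bin(k, 0.60 + D).

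| k | D (points) | Bias (points) | Chi-square, uncorrected | Fisher |
|---|---|---|---|---|
| 0 | – | 0 | 5.69% | 3.52% |
| 5 | +10 | 5/52 × 10 = 0.96 | 5.75% | 3.55% |
| 10 | +15 | 10/52 × 15 = 2.88 | 6.58% | 4.16% |
| 20 | +15 | 20/52 × 15 = 5.77 | 9.80% | 6.54% |
| 20 | +20 | 20/52 × 20 = 7.69 | 13.22% | 9.13% |

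The uncorrected chi-square test is already slightly above 5% at k=0, so that row is the right comparator. With D negative, the chi-square rates for the same four combinations are 5.84%, 6.85%, 10.33% and 13.88%.

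**If they had been counted among the 52 and are removed.** There are 52 TSM patients and 52 − k controls. The power formula is as above, with the pooled rate and both standard errors recomputed. The 95% CI half-width is 1.96 × √(0.25/52 + 0.1875/(52 − k)).

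| k | Controls left | Power | CI half-width (points) |
|---|---|---|---|
| 0 | 52 | 75.7% | 18.0 |
| 10 | 42 | 70.5% | 18.9 |
| 20 | 32 | 62.8% | 20.2 |

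**The case against.** The strongest reply is that the SAP already answers the question. Patients placed directly in standard of care were not randomized, so a set of all subjects randomized leaves them out. On the literal words that is right. It does not settle the matter, because the protocol describes the same patients as randomized and the SAP never acknowledges that one arm closed.

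Harm also needs two things the documents do not establish: that anyone enrolled after closure, and that such patients were analyzed as controls. That stands, and it is why the size is given as a range starting at zero.

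The large values of k have no direct support. If TSM closed on reaching its planned number, permuted blocks would leave the arms nearly equal, and the shortfall in controls might be about 58 − 52 = 6. That is plausible, but the reason for closure is not given. On a base of 58 controls the bias is also smaller (20/58 × 20 = 6.9 points instead of 7.7), and removing 6 of 58 would still leave 52. So the power loss shown applies only if these patients were counted toward the 52.

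The protocol does plan secondary analyses adjusted for demographic, comorbidity and functional variables. The list does not include calendar time, cannot cover unmeasured selection, and does not protect the unadjusted primary test.

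Finally, a plan written before enrollment could not state k. But the recruitment text already knows that TSM has closed and the SAP is written in the past tense, so asking for the date and the count is fair.

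**Conclusion.** The concern holds and needs correction. The recruitment text contradicts itself and the rest of the protocol. Followed as written, it places non-randomized, non-concurrent patients in the control arm. The SAP's analysis set does not say clearly that they are excluded.

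This does not show that bias occurred. Under the assumptions above, a handful of such patients is nearly harmless, while 20 of 52 with a risk 15 to 20 points different would bias the comparison by 5.8 to 7.7 points, against a planned difference of 25, and take the chi-square false-positive rate from 5.7% to about 10 to 14%, depending on direction. The contradiction is certain. The size of its effect depends on a count that the documents do not give.

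**What to change.** 1. Reconcile Recruitment Procedures with the Specific Aims, the Experimental Design, the sample size paragraph and the SAP, so that patients enrolled after TSM closed are not described as randomized.
2. Define the primary intention-to-treat set in the SAP as patients allocated from the biostatistics unit's schedule while both arms were open.
3. Record the TSM closure date, an enrollment-period flag, and the number enrolled to standard of care only, saying so if it is zero.
4. Show those patients only descriptively or in a labelled sensitivity analysis.
5. If any had been counted toward the 52 controls, restate the control sample size and the power.

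The cost is wording in two documents and one data flag. If the count is zero, one sentence closes the point and nothing is lost. If not, the primary comparison gives up those patients, with the loss of power and precision shown in the second results table.

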Inclusion Criteria for CHF Patients and CHF patient focus group: 1) CHF patients about to be discharged from NUMC or within a week from discharge; 2) 18 years and older; 3) NYHA class of 1-3; 4) primary language of Spanish or English; 5) access to a phone (land line or cell); 6) Folstein MMSE score of 21 or higher; 7) anyone who self identifies as Black/Latino/multiracial (must include black or Hispanic). We will also conduct a focus group with the initial 10 patients enrolled in the intervention arm of the study to obtain user feedback regarding any barriers to implementation or usability suggestions to further adapt the intervention if necessary before additional participants are enrolled.

Inclusion criteria for CAB focus groups: The CAB will consist of CHF patients (and caregivers in the community and stakeholders (individuals) within the community with whom the PI has already forged relationships, in addition to members of the NUMC advisory board; Inclusion criteria for patients participating the CAB focus group are: patients with CHF, NYHA class 1-3 and at least 18 years old. No inclusion or exclusion criteria for the other member of the CAB group, such as stakeholders and caregivers.

Exclusion Criteria for CHF patients and patient focus group: 1) seniors with heart failure NYHA class 4 (because they are primarily bed-bound and highly unlikely to be able to participate in the tasks required for the intervention); 2) Anyone under age 18; 3) Anyone with no access to a phone; 4) Anyone with a primary language that is not English or Spanish; 5) Anyone with a Folstein MMSE score under 21 (indicative of cognitive impairment); 6) Anyone who declines consent; 7) Anyone who does not identify as Black/Latino/multiracial; 8) Patients who have chosen a home care agency that provides telehealth monitoring. Therefore, patients will be contacted and enrolled only after they have chosen their home care agency.

No exclusion criteria for members of the CAB group.

RECRUITMENT PROCEDURES

Individuals participating in the focus groups and CAB will consist of patients with CHF, caregivers and patient's stakeholders in the community with whom the PI has already forged relationships in addition to members of the NUMC advisory board. Drs. [name] and [name] will review the consent form with these individuals and consent will be obtained if the subject is willing to be part of the study.

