Secondary Analyses: Adjusting for Confounders: Potential confounders will be demographic (age, gender, race, ethnicity, primary language spoken, insurance status (insured vs notinsured), education (high school graduate vs. non-graduate), major co-morbidities (e.g., diabetes Y/N) and functional variables (e.g., heart class, depression symptoms, anxiety symptoms, and caregiver support). All of these measures will be assessed at baseline only. We will use the PHQ4¹⁹ (Appendix 5) to assess symptoms of depression and generalized anxiety disorder as both of these are factors known to have direct impact on cardiovascular outcomes.²⁹ This is a brief measure (with limited potential participant burden) that has been validated and widely used with heart failure patients.^{30,31} It has also been translated into Spanish.^{32,33} We will also use a brief measure of caregiver support that assesses assistance with heart failure medical care. The stem question asks if there is someone in participants' lives who helps with heart failure medical care and if answered in the affirmative, participants then indicate their relationship with that person and whether the person lives in the home (Appendix 6). To this end, multiple logistic regression will be used where the outcome variable is hospitalization (yes/no) and the predictor variables are treatment group (telehealth vs. control) on the aforementioned covariates. For number of hospitalizations and length of stay (LOS), analysis of covariance (ANCOVA) will be used if the required distributional assumptions can be met. If not, extension of Lachenbruch's procedure using logistic regression and analysis of variance will be used.

CONFIDENTIALITY

Confidentiality will be protected by assigning to each subject a research data a unique identifier known only to IRB approved personnel.

Storing Documents in Hard Copy

Any documents that contain PHI (e.g., consent forms, link between the ID to subjects' identifiers) will be stored in a locked cabinet within the office of the principal investigator, separately from any de-identified research documents. IRB approved personnel will be the only individuals with access to any research documents containing PHI.

Storing Documents Electronically

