ED utilization was defined as whether or not an individual patient had at least one ED visit over the 90-day period. Binary outcomes for ED visits and hospitalizations were analyzed using the standard Chi-square or Fisher's exact test. Associated 95% confidence intervals for these proportions and their differences were computed using exact methods. The number of ED visits as well as hospitalizations within each group were separately compared using Poisson regression (SAS PROC GENMOD). Due to excess zeros (i.e., zero inflation), methods for over dispersed Poisson were required for both ED visits and hospitalizations. Cumulative LOS (inpatient days) was analyzed using a negative binomial regression. HF-related hospitalizations, ED visits, and LOS were analyzed in the same fashion described above, as were cardiovascular related outcomes. Reasons for ED visits as well as hospitalizations were classified as: HF alone (yes/no), cardiovascular related alone (yes/no), or both by the clinical team.

Repeated measures analysis of variance (RMANOVA) with a mixed models approach was used to compare changes at enrollment and at 90 days between groups. New York Heart Association (NYHA) class, PHQ-4, MLHFQ Physical and Emotional subscales were also analyzed using RMANOVA. The subscales of Anxiety and Depression, as measured by the PHQ-4, were dichotomized to presence or absence and Generalized Estimating Equations (GEE) were used to analyze these binary data. Days at home was

calculated as a proportion of days spent out of hospital during the 90 day period. The two groups were compared using the Mann-Whitney test.

Subgroup analyses included: patients hospitalized, heart class (2 vs. 3), and patients not receiving home care (prevalent in disparity populations). For the TSM group only, adherence was calculated, with low adherence defined as less than 10 vital signs uploads over the 90 day period.

Sample size and power calculations were based on previous literature and preliminary data from a non-disparity randomized RCT TSM study. We hypothesized that 75% of patients in the COM group would be hospitalized at least once during the study period and that TSM would reduce that rate to 50% (a relative reduction of 50%). The calculation was based on a chi-square test (alpha=0.05, two-tailed) with an n=52 patients per group. All analyses were performed using SAS 9.4 (SAS Institute Inc., Cary, NC).

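### The protocol promises gender balance by block randomisation, but the SAP stratifies by heart class only; the factors must be reconciled and the analyses should use them

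*Protocol*

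**What the plan says.** **Allocation.** The protocol, under Recruitment Procedures, names two balancing factors: "We will conduct a block randomization technique to ensure equivalency of gender and Heart Class 3 patients across the two groups". It assigns the randomisation to the Biostatistics Unit. The SAP's opening paragraph, describing that unit's schedule, says patients were allocated "using permuted block randomization, with stratification by heart class, to ensure equal representation of heart class across the two groups". The SAP thus gives both a factor and its purpose, and gender is in neither. Neither document states a block size.

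**Levels of heart class.** The protocol balances class 3. The SAP gives no levels for the stratum. Eligibility is "3) NYHA class of 1-3", while the SAP's subgroup analysis contrasts class 2 with class 3: "Subgroup analyses included: patients hospitalized, heart class (2 vs. 3), and patients not receiving home care".

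**Analysis.** For inpatient utilisation the protocol says: "For these primary ITT analyses, no adjustments will be made for any covariates". Its section on secondary analyses then lists gender among the variables to adjust for ("Potential confounders will be demographic (age, gender, race, ethnicity, primary language spoken, insurance status") and also lists heart class. It specifies logistic regression for hospitalisation, and ANCOVA or an extended Lachenbruch procedure for number of hospitalisations and length of stay. Section 2b promises covariate adjustment for ER outcomes. The SAP lists chi-square or Fisher tests, overdispersed Poisson, negative binomial, repeated-measures, GEE and Mann-Whitney analyses, and states no covariate or stratum term for any of them.

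**The concern.** Both texts describe one schedule from one unit, yet they list different factors, and nothing in either document explains the difference. Either gender was not a factor, and the protocol claims a balance that the schedule does not enforce, or it was, and the SAP's description is incomplete.

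A reader needs to know which. The factors determine what baseline balance to expect, how the allocation is to be reported, and which terms belong in a stratified analysis. In a trial of about 104 patients, chance imbalance on an unstratified binary factor is not rare. The protocol itself regards gender as a potential confounder, and the SAP drops the adjusted analysis that would have dealt with it.

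**Working it through.** There is no stated figure to reproduce. The check compares the texts and then sizes the imbalance that heart-class stratification alone would leave.

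**Inputs**
- Patients per arm: 52, from the SAP ("The calculation was based on a chi-square test (alpha=0.05, two-tailed) with an n=52 patients per group"); total 104.
- Share of women: not given in the documents; assumed 30% to 60%, that is 31, 42, 52 or 62 women of 104.
- Block size: not given; 4 is assumed where one is needed.

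**Imbalance without gender stratification**

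Let F be the total number of women and X the number in one arm. As an approximation that ignores any association between gender and heart class, X is hypergeometric (104 patients, F women, 52 drawn). The difference in proportions is (2X − F)/52.

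Its variance follows from Var(X) = 52 × (F/104) × (1 − F/104) × 52/103. For F = 52 this is 52 × 0.5 × 0.5 × 52/103 = 6.56, so SD(X) = 2.56 and the SD of the difference is 2 × 2.56/52 = 0.099, about 10 percentage points.

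| Women of 104 | SD of difference | P(≥ 10 points) | P(≥ 15 points) | P(≥ 20 points) |
|---|---|---|---|---|
| 31 (30%) | 0.090 | 0.198 | 0.085 | 0.031 |
| 42 (40%) | 0.097 | 0.318 | 0.161 | 0.027 |
| 52 (50%) | 0.099 | 0.327 | 0.170 | 0.030 |
| 62 (60%) | 0.097 | 0.318 | 0.161 | 0.027 |

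The counts are discrete. Ten points of 52 is 5.2 women, so with an even F the smallest qualifying difference is 6 women, and with an odd F it is 7. Part of the drop in the first row comes from this: with F = 32 instead of 31, the same calculation gives 0.288. The range of 20% to 33% should be read as approximate. The protocol also speaks of randomising 58 per arm to yield 52. With 58 per arm and 30% to 60% women (35, 46, 58 or 70 of 116), the chance of at least 10 points is 0.225 to 0.353, so the conclusion does not depend on which count is used.

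**Imbalance if gender were also a stratum**

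With blocks inside each gender-by-heart-class cell, the largest difference in the number of women is (heart-class strata) × (block size/2). For an assumed block of 4:
- two heart-class strata: 2 × 2 = 4 women, 4/52 = 7.7 points;
- three heart-class strata: 3 × 2 = 6 women, 6/52 = 11.5 points.

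These are worst cases; typical differences would be smaller.

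**What an imbalance could do to the treatment contrast**

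The documents give no association between gender and hospitalisation. Assume the risk differs by 5 to 20 points between women and men. A gender imbalance of 10 to 15 points then shifts the treatment difference by 0.10 × 5 = 0.5 points to 0.15 × 20 = 3 points, against the SAP's hypothesised 75% − 50% = 25 points.

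**The case against.** The case for leaving this alone has four parts.

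1. **The SAP may only be incomplete.** It is a short, past-tense methods text and does not say that heart class was the sole factor. That is fair. A reader might infer that gender was dropped from the schedule, but the documents do not show it. They show only that the descriptions differ.

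2. **The inference is sound either way.** This stands. Randomisation within heart class is valid without gender as a stratum, and the test's error rate already allows for chance imbalance. If gender was a stratum, ignoring it generally makes the unadjusted tests conservative. A reader might infer an invalid comparison or an inflated false-positive rate; neither follows.

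3. **The protocol already handles gender.** Largely true of the protocol: it plans gender-adjusted secondary models for hospitalisation, and covariate adjustment for ER outcomes. It would be wrong to say that the comparison is left without any protection. But the SAP contains none of these models, and neither document gives an explicit adjusted model for QoL.

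4. **Gender stratification guarantees less than it seems.** Also true: with three heart-class strata and blocks of 4, the worst case is 11.5 points. That weakens the protocol's claim to ensure equivalency; it does not reconcile the two texts.

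The same protocol section also says that patients are to be told the telehealth arm has closed and that they will enter standard of care. That may matter more for comparability than gender does, but it is a separate issue and does not settle which factors the schedule used.

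**Conclusion.** The documents disagree on the randomisation factors, and on the SAP's description gender balance is left to chance. The arms would then differ by at least 10 points in about 20% to 33% of trials, given 52 per arm and an assumed 30% to 60% women. The likely effect on the treatment contrast is small: 0.5 to 3 points under the assumed gender–hospitalisation association.

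This is a modest but real fault in three parts: a claimed balance property that the schedule may not have; primary analyses that ignore the stratification factors, with a possible loss of precision; and protocol-planned gender adjustment that the SAP omits. The second part does not depend on how the gender question is settled. Heart class is a balancing factor in both documents, yet in the SAP it enters no main between-arm comparison and serves only to define a subgroup analysis.

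**What to change.** 1. Take the stratification factors, their levels and the block size from the Biostatistics Unit's actual schedule, and state them identically in both documents. Say which heart classes form the strata.

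2. Analyse by the factors used: heart class in either case, plus gender if it was a stratum. A Cochran-Mantel-Haenszel test or a logistic model would serve for the binary hospitalisation and ED outcomes, with stratum terms in the count, length-of-stay and QoL models.

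3. If gender was not a stratum, delete the gender-equivalency claim from the protocol, report gender by arm, and carry the protocol's gender-adjusted analysis into the SAP for hospitalisation, ED and QoL as a secondary or sensitivity analysis.

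**Cost.** Short text corrections in both documents and some extra analysis; the protocol already plans to record gender and heart class at baseline. The price is that the unadjusted chi-square or Fisher test, which takes no covariate, becomes supportive. If the data have already been seen, as the SAP's past tense suggests is possible, the unadjusted test keeps its place and the stratified analysis is labelled as sensitivity.
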